3. STUDY OBJECTIVES

3.1 PRIMARY OBJECTIVES

- To evaluate the safety and tolerability of the VRC-FLUNPF099-00-VP vaccine, administered as a single dose at 20 mcg IM via needle and syringe on Day 0 to healthy adults.
- To evaluate the safety and tolerability of the VRC-FLUNPF099-00-VP vaccine, administered at 60 mcg IM via needle and syringe to healthy adults by repeat dosing on Day 0 and Week 16 for a total of 2 injections.

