4.3 CRITERIA FOR DOSE ESCALATION AND DOSE CONTINUATION

There will be one dose escalation review and two dose continuation reviews in this study. The Protocol Safety Review Team (PSRT, Section 8.8) will conduct an interim safety data review before dose escalation or repeat dosing may occur. The PSRT must assess the data as showing no

significant safety concerns before enrollment of the next dose level and repeat dosing at the same level may proceed.

Enrollment will begin in Group 1 (20 mcg of VRC-FLUNPF099-00-VP) with no more than one subject enrolled per day. Two weeks after vaccination of the third subject, there will be an interim safety review of available data for three subjects to determine whether to continue enrollment in Group 1 and to proceed to the next dose level. If the 20 mcg dose of VRC-FLUNPF099-00-VP is assessed as safe, enrollment can continue for Group 1 and begin for Group 2A.

In Group 2A (60 mcg of VRC-FLUNPF099-00-VP), enrollment will continue with no more than one subject enrolled per day. Two weeks after vaccination of the third subject, there will be an interim safety review of the available data for three subjects to determine whether to proceed to Groups 2B, 2C, and 2D. If the 60 mcg dose of VRC-FLUNPF099-00-VP is assessed as safe, enrollment can continue for Group 2A and begin for Groups 2B, 2C, and 2D. Additionally, if the 60 mcg dose is assessed as safe, all Group 2 subjects may receive the second vaccination at week 16.

Additional subjects may be enrolled into a group in order to have the requisite data for at least 3 subjects, if first vaccinations are not completed or there are discontinuations from the study before there are sufficient data to conduct the dose escalation and continuation review for that group.

The IRB will be provided with documentation of the safety review process and notification of the dose escalation. Consultation with the IRB and FDA, if needed, as per study pause criteria (Section 4.5) will occur if indicated by the review. One outcome of a dose escalation review may be to recommend evaluation of additional subjects at the current dose level and reassess for safety before proceeding to a higher dose level and repeat dosing at the same dose level.

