4.5 CRITERIA FOR PAUSING AND RESUMING THE STUDY

4.5.1 Plan for Pausing the Study

The PI and Protocol Safety Review Team (PSRT) will closely monitor and analyze study data as they become available and will make determinations regarding the presence and severity of AEs. The administration of study injections and new enrollments will be paused and the IND Sponsor will be promptly notified according to the following criteria:

- **One** (or more) subject experiences a **SAE** or **Grade 4 AE** assessed as related to study product.
- **Two** (or more) subjects experience the same **Grade 3 unsolicited AE** assessed as possibly, probably or definitely related to study product.
- **Three** (or more) subjects experience the same **Grade 2 or higher laboratory abnormality** assessed as possibly, probably or definitely related to study product.
- **One** (or more) subject experiences ulceration, abscess, or necrosis at the injection site.

Self-limited solicited reactogenicity that is not an SAE will not be counted towards pause criteria.

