6.2 ENDPOINTS

6.2.1 Primary Endpoints: Safety

Assessment of product safety will include clinical observation and monitoring of hematological and chemical parameters. Reactogenicity will be closely monitored for 7 days after each injection and safety evaluated by clinical visits for 52 weeks following the last vaccine administration and through an influenza season. See Section 4.2 and Appendix I for details and specified time points. The following parameters will be assessed for all study groups:

- Occurrence of solicited local reactogenicity symptoms for 7 days after each injection
- Occurrence of solicited systemic reactogenicity symptoms for 7 days after each injection
- Change from baseline in safety laboratory measures

- Occurrence of AEs of all severities through the 4 week post-injection visit
- Occurrence at any time throughout the study of SAEs or new chronic medical conditions that require ongoing medical management.

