8.5 RISKS AND BENEFITS

8.5.1 Risks of the VRC-FLUNPF099-00-VP vaccine

This is the first study in humans of the investigational vaccine, VRC-FLUNPF099-00-VP. This product is derived from *H. pylori* ferritin and not human ferritin, for this reason it is not expected to interfere with iron storage, transport or iron serum levels [18].

Potential side effects resulting from IM injection include stinging, arm discomfort, redness of the skin or mild bruising at vaccine injection sites.

Subjects may exhibit general signs and symptoms associated with administration of a vaccine, including fever, chills, rash, aches and pains, nausea, headache, dizziness and fatigue. These side effects will be monitored, but are generally short term, mild to moderate severity and

usually do not require treatment.

In another VRC study of a similar ferritin vaccine (VRC 316), only 23.4% of participants were noted to have occasional asymptomatic and self-limited changes in laboratory tests such as mild leukocytosis, mild leukopenia, and mild increase in ALP as of March 24, 2019.

There may be other unknown side effects.

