Research Samples																								
H. pylori ferritin antibody and human ferritin antibody	X				X								X											
Serum	32	16		16	16	16	16		16		16	16	16	16	16	16	16							
PBMC and plasma	80	80		80	80	80	80		80		80	⁷ 120 or Apheresis (6)	80	80	80	80	80							
Daily Volume (mL)	122	103	0	96	103	103	96	103	103	0	96	136	103	116	103	103	103							
Max. Cumulative Volume (mL)	122	225	225	321	424	527	623	726	727	822	958	1,061	1,177	1,280	1,383	1,486	1,486							

* VRC 500: Screening evaluations must be no more than 28 days prior to Day 0 to be used for eligibility (pregnancy test from Day 0 must be used for eligibility). If clinical assessment on Day 0 suggests significant changes may have occurred since screening, then physical examination & laboratory studies done on Day 0 are used for eligibility.

¹ Day 0=day of enrollment and first vaccine injection. Day 0 evaluations prior to first injection are the baseline for assessing adverse events subsequently.

² Screening visit includes physical exam with vital signs. At other visits, physical examination is done if indicated. Otherwise only blood pressure (BP), pulse, temperature, and respiration are required.

³ Study Product Administration: Groups 2A-2D will receive H1ssF_3928 60 mcg IM at Day 0 and Week 16. Complete post vaccination evaluations (BP, pulse, temperature, respiration and injection site assessment) at 30 minutes or longer after each injection for Group 2A-2D.

⁴ Negative pregnancy test results must be confirmed for women of reproductive potential prior to each study injection and prior to apheresis.

⁵ HLA type blood sample is collected once at any time-point in the study and is shown as a Visit 05 evaluation for convenience; however, if HLA type is already available in the medical record, it does not need to be repeated. HLA type may also be obtained from a frozen sample.

⁶ Visit 03: Two EDTA tubes for PBMC collected will be sent to Building 40, while the remainder of the blood collected will be sent to VIP.

⁷ If optional Apheresis occurs, ONLY draw 16 mL in SST (DO NOT draw 120 mL in EDTA tubes).

⁸ For women of reproductive potential, pregnancy test must be negative within 72 hours prior to apheresis procedure.

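### In Groups 2A-2D the first scheduled safety labs after dose 2 come at 4 weeks, against 2 weeks after dose 1, so short-lived laboratory changes after the second dose can be missed

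*Combined protocol and SAP*

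**What the plan says.** Section 3.1 makes the safety of the 60 mcg regimen a primary objective, "by repeat dosing on Day 0 and Week 16 for a total of 2 injections". Section 6.2.1 lists "Change from baseline in safety laboratory measures" among the primary endpoints. It gives that endpoint no time points of its own and sends the reader to Appendix I, so the schedule decides when it is measured.

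In the Appendix I table for Groups 2A-2D, the injections are at Visit 02 (D0) and Visit 07 (D112). The 2-week visits are Visit 04 (D14) and Visit 09 (D126), and the 4-week visits are Visit 05 (D28) and Visit 10 (D140). A CBC (3 mL) and a liver panel (4 mL) are scheduled at Visits 04, 05 and 10, but not at Visits 08 and 09. Visit 09 has a larger research draw of 120 mL, or optional apheresis. Footnote 7, attached to that research cell, reads "If optional Apheresis occurs, ONLY draw 16 mL in SST (DO NOT draw 120 mL in EDTA tubes".

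The laboratory pause rule in section 4.5.1 is met when three or more subjects have the same "Grade 2 or higher laboratory abnormality" judged related to the product. Section 8.5.1 says that an earlier ferritin vaccine produced "occasional asymptomatic and self-limited changes in laboratory tests such as mild leukocytosis, mild leukopenia, and mild increase in ALP". The documents give no reason for the different laboratory schedules after the two doses.

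**The concern.** Other safety collection treats the two injections alike: a 7-day diary after each, and all unsolicited adverse events recorded to the 4-week visit after each (section 5.1). Laboratory events are different because most are found only by testing. With two panels in the 4 weeks after dose 1 and one after dose 2, the same recording window has unequal ascertainment.

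The changes reported for the earlier ferritin vaccine were asymptomatic, so symptoms would not be expected to prompt an unscheduled test. Two things are at stake:

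- A change that arises and clears before Visit 10 would not appear in the scheduled data for dose 2.
- A change that persists would be seen about 14 days later than the same change after dose 1. Enrollment is staged, so other subjects could receive dose 2 in that interval.

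**Working it through.** **Step 1. Which visits carry a safety panel.** Inputs are from the Group 2 table in Appendix I: serum 16 mL, research EDTA 80 mL (120 mL at Visit 09), CBC 3 mL, liver panel 4 mL.

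| Visit | Timing | Sum of tubes (mL) | Printed daily volume | Cumulative | Panel? |
|---|---|---|---|---|---|
| 04 | 2 wk after dose 1 | 16 + 80 + 3 + 4 = 103 | 103 | 321 to 424 | yes |
| 05 | 4 wk after dose 1 | 16 + 80 + 3 + 4 = 103 | 103 | 424 to 527 | yes |
| 08 | 6 days after dose 2 | 16 + 80 = 96 | 96 | 726 to 822 | no |
| 09 | 2 wk after dose 2 | 16 + 120 = 136 | 136 | 822 to 958 | no |
| 10 | 4 wk after dose 2 | 16 + 80 + 3 + 4 = 103 | 103 | 958 to 1,061 | yes |

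With a panel, Visit 09 would be 143 mL and the running total 965, not 958. All 16 visits sum to the printed total: 122 + 103 + 0 + 96 + 103 + 103 + 96 + 103 + 0 + 96 + 136 + 103 + 116 + 103 + 103 + 103 = 1,486 mL.

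The Visit 07 panel is not a post-dose-2 panel, because section 4.2.5 requires scheduled blood to be drawn before the injection.

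The table text available for this review has displaced columns. The CBC and liver rows show 10 entries where the volumes support 9, and the daily-volume row repeats one 103 around Visit 07. The cumulative row shows 727 at Visit 07A, where 726 + 0 = 726. I do not count these as errors in the plan. Aligned from the right, the CBC and liver cells are blank at Visits 08 and 09 and filled at Visit 10, which agrees with the volumes.

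**Step 2. Length of the gap.** Both the 2-week and the 4-week visits have windows of ±2 days. The first scheduled panel comes at day 14 (12 to 16) after dose 1 and at day 140 - 112 = 28 (26 to 30) after dose 2.

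**Step 3. Illustration of size.** Let X be the number of 48 Group 2 subjects with the same related Grade 2 or higher change, present at week 2 and gone by week 4. Take X as binomial(48, p), with p assumed. Table 6-1 (N=48) gives P(more than 1), and these values were reproduced. Then P(X ≥ 3) = P(X > 1) - P(X = 2), where P(X = 2) = 1,128 p²(1 - p)⁴⁶.

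| Assumed p | Expected cases | P(X > 1), Table 6-1 | P(X = 2) | P(X ≥ 3) with a week-2 panel | From scheduled labs after dose 2 now |
|---|---|---|---|---|---|
| 0.02 | 0.96 | 0.249 | 0.178 | 0.071 | 0 |
| 0.05 | 2.4 | 0.699 | 0.266 | 0.433 | 0 |
| 0.10 | 4.8 | 0.960 | 0.089 | 0.871 | 0 |

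The lowest rate is close to the only related rates in the documents: three mild events with the earlier ferritin vaccine, each in 1/47 = 2.1% (section 1.3.1). For a change still present at day 28, Visit 10 gives the same probabilities as a week-2 panel, about 2 weeks later.

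**The case against.** The best defence is that dose 2 is not unobserved. Visit 10 carries CBC, liver tests, creatinine, iron and ferritin, and panels follow at Visits 12 to 14. Visits 08 and 09 include history and vital signs, and apheresis volunteers have a hemoglobin check. Laboratory results are summarised by descriptive plots, and no formal comparison between doses is planned. All of this stands and limits the point to short-lived or late-seen changes. It does not explain why the 2-week panel is dropped.

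A reader might infer more than the documents support:

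- **That the two doses cannot be compared on laboratory safety.** Visits 05 and 10 are matched 4-week panels with the same window.
- **That footnote 7 forbids safety tubes.** It belongs to the research cell and cancels the 120 mL EDTA draw. Section 4.2.10 lets a clinician request other samples before apheresis. The evidence is in the laboratory and volume rows.
- **That the 2-week safety review requires a Visit 09 panel.** Section 4.3 says "Two weeks after vaccination of the third subject, there will be an interim safety review of the available data for three subjects", but this concerns first vaccinations. It may explain the schedule after dose 1, though the documents do not say so.
- **That the earlier vaccine's record supports high rates.** Its three related laboratory events were mild and all different. The 23.4% in section 8.5.1 covers any such change. Grade 2 anaemia occurred in five subjects but is not among the events judged related.
- **That apheresis or the larger draw would distort the Visit 10 panel.** Section 4.2.10 puts the red cell loss at apheresis at the equivalent of 6 mL. The Visit 09 draw is only 136 - 103 = 33 mL more than the draw that precedes Visit 05.

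**Conclusion.** The asymmetry is real and unexplained: two scheduled panels within 4 weeks of dose 1, one within 4 weeks of dose 2. The primary laboratory endpoint and the laboratory pause rule therefore have less ascertainment after the second dose. The repeat-dose objective can still be addressed, because persistent changes are captured at Visit 10 and later.

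The probabilities of 7%, 43% and 87% illustrate the mechanism and do not estimate this vaccine's behaviour. They assume the event rates, independent events, all 48 subjects dosed twice and sampled, every event Grade 2 or higher and related, and resolution between weeks 2 and 4. The documents give no duration for such changes; if all last beyond week 4, the loss is delay only. The pause rule also counts subjects without regard to dose, so cases found after dose 1 still count. The zero refers only to what scheduled tests after dose 2 would add. This is an inexpensive improvement to ascertainment and not a flaw that undermines the trial.

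**What to change.** In the Group 2 table, add to Visit 09 the same CBC with differential and bilirubin/AST/ALT/ALP panel that is taken at Visit 04, drawn before any apheresis. Reword footnote 7 so that it cancels only the 120 mL research EDTA draw and not the safety tubes. Keep the panels at Visits 12 to 14 in the laboratory endpoint; do not relabel it as weeks 2 and 4 only. If the sponsor prefers the present schedule, state the reason for the difference.

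The cost is one routine panel and 3 + 4 = 7 mL per Group 2 subject, with no new visit. Visit 09 rises from 136 to 143 mL, or from 16 + 6 = 22 to 29 mL with apheresis. The maximum cumulative volume rises from 1,486 to 1,493 mL (7/1,486 = 0.5%). The blood-volume ceiling is not given in the documents and should be checked. In subjects without apheresis the change can be volume-neutral by cutting the research draw to 113 mL (113 + 16 + 7 = 136), about 6% less research EDTA blood at that visit.
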